6.5.3. Concomitant Medications and Nondrug Treatments

All prior and concomitant medication(s) as well as non-drug treatment(s) will be provided in listings.

6.6. Safety Summaries and Analyses

Any clinical laboratory, ECG, BP, and pulse rate abnormalities of potential clinical concern will be described.

No formal analyses are planned for safety data.

The safety endpoints detailed in [Section 3.5](#) will be listed and summarized in accordance with sponsor reporting standards based on the safety population (as defined in [Section 4](#)), with more details provided below.

6.6.1. Adverse Events

Adverse events will be summarized by treatment and overall in accordance with sponsor reporting standards.

If applicable, subject discontinuations due to adverse events will be detailed and summarized.

6.6.2. Laboratory Data

Laboratory data will be listed and summarized by treatment and overall in accordance with sponsor reporting standards. Baseline is as defined in [Section 3.5](#).

6.6.3. Vital Signs

Absolute values and changes from baseline in supine systolic and diastolic blood pressure and pulse rate will be summarized by treatment in accordance with sponsor reporting standards.

Maximum absolute values and changes from baseline for vital signs will also be summarized descriptively by treatment using categories as defined in Appendix 2. Numbers and percentages of participants meeting the categorical criteria will be provided. All planned and unplanned post-dose time-points will be counted in these categorical summaries. All values meeting the criteria of potential clinical concern will be listed.

6.6.4. Electrocardiograms (ECG)

Absolute values and changes from baseline in QT interval, heart rate, QTcF interval, PR interval, and QRS interval will be summarized by treatment in accordance with sponsor reporting standards.

Maximum absolute values and changes from baseline for QTcF interval, PR interval and QRS interval will also be summarized descriptively by treatment using categories as defined by Appendix 2. Numbers and percentages of participants meeting the categorical criteria will be provided. All planned and unplanned post-dose time-points will be counted in these categorical summaries. All values meeting the criteria of potential clinical concern will be listed.

In addition, listings of participants with any single post-dose value >500 msec will also be produced for QTcF.

In addition, the number of participants with uncorrected QT values >500 msec will be summarized.

7. INTERIM ANALYSES

7.1. Introduction

No formal interim analysis will be conducted for this study. As this is an open-label study, the sponsor will conduct unblinded reviews of the data during the course of the study for the purpose of safety assessment, early release criteria, facilitating PK modeling, and/or supporting clinical development.

7.2. Interim Analyses and Summaries

Not applicable.

8. REFERENCES

Not applicable.

9. APPENDICES

Appendix 1. Example SAS Code for Mixed Model

An example of the PROC MIXED code:

```
proc mixed data=tab.pk;
  class treatment subject;
  model &var = treatment / ddfm=KR;
  random subject /subject=subject;
  lsmeans treatment/ diff cl alpha=0.1;
run;
```

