4.2. Scientific Rationale for Study Design

A fixed sequence, open-label, study design has been chosen to minimize intra-individual variability and enable within-participant comparison of the urinary excretion of radioactivity with both oral and IV routes for the estimation of F_a . As is common for Phase 1 studies, the population envisioned for this study is healthy participants. Only males will be included in this study given the desire to enroll a homogeneous population due to the small sample size of this study.

Available PK data with PF-07081532 administered under fasted or fed conditions indicate that PF-07081532 may be administered without regard to food. In this study, dosing of PF-07081532 is planned to occur in the fed state, with standard breakfast in both periods, as described in [Section 5.3.2](#), to reflect the conditions for anticipated use of PF-07081532 in future trials and the target patient population.

In this study, a “microtracer” approach will be used where the [^{14}C] dose is much lower than in conventional ADME studies. With this approach, [^{14}C] will be quantified using an AMS detection technique. This technology allows ADME studies to be conducted without WBA data, as concentrations of [^{14}C] and resulting exposures are so minute that dosimetry calculations are not needed.

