9.5. Sample Size Determination

A sample size of approximately 6 participants has been chosen based on the industry standard sample size for mass balance and radiolabeled microtracer studies and in line with latest FDA draft guidance (May 2022).⁹ This sample size was not chosen based on any empirical data or hypothesis testing criteria. The sample size has been selected to ensure that 6 participants provide evaluable data after completing Period 1; with intent to replace participants who prematurely withdraw (or offer non-evaluable or partially evaluable data). In Period 2, participants who are prematurely withdrawn may be replaced at the discretion of sponsor.

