5.2.3. Mixed Model for Continuous Endpoints

A *mixed effect model with treatment as a fixed effect and participant as a random effect* will be used. *Estimates of the adjusted (least squares) mean differences (Test-Reference) and the corresponding 90% confidence interval will be obtained from the model. The adjusted mean differences and 90% confidence intervals for the differences will be exponentiated to provide estimates of the ratio of adjusted geometric means (Test/Reference) and 90% confidence interval for the ratio.*

The mixed effects model will be implemented using SAS Proc Mixed, with REML estimation method and the Kenward-Roger degrees of freedom algorithm.

Example code is shown in Appendix 1.

Residuals from the models will be examined for normality and the presence of outliers via visual inspection of plots of residuals vs predicted values and normal probability plots of residuals but these will not be included in the clinical study report. If there are major deviations from normality or outliers (where studentized residuals are greater than 3 or less than -3) then the effect of these on the conclusions may be investigated through alternative transformations and/or analyses excluding outliers. Justification for any alternative to the planned analysis will be given in the report of the study if applicable.

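### With about six pairs and a participant variance bounded at zero, the 90% CI for Fa (and, less so, F) can fall somewhat short of nominal coverage; the SAP has no rule for a zero estimate.

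*SAP*

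**What the plan says.** SAP 5.2.3 analyses the log-transformed values with a "mixed effect model with treatment as a fixed effect and participant as a random effect" and fixes the software: "The mixed effects model will be implemented using SAS Proc Mixed, with REML estimation method and the Kenward-Roger degrees of freedom algorithm". SAP 6.2.2 (F) and 6.2.3 (Fa) both refer back to this model.

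Appendix 1 gives example code. The procedure call is "proc mixed data=tab.pk", with "model &var = treatment / ddfm=KR", "random subject /subject=subject" and "lsmeans treatment/ diff cl alpha=0.1". NOBOUND does not appear.

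On model checking, SAP 5.2.3 covers residual normality and outliers. Neither document says what happens if the participant variance is estimated as zero, and neither gives a within-participant correlation or variance.

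On size, Protocol 9.5 says "A sample size of approximately 6 participants has been chosen" and states that the number does not come from data or a test criterion. Replacement in Period 2 is at the sponsor's discretion, so fewer than six pairs is possible.

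**The concern.** Each man contributes an oral and an IV value, and Protocol 4.2 chose the design so that the two could be compared within participant. With so few pairs, the between-participant mean square can fall below the within-participant one by chance, even when the true participant variance is positive. A bounded fit then sets the variance to zero and analyses the 12 values as independent. In those trials the interval is always narrower than the paired one. In all other trials it equals the paired one. Average coverage must therefore be below that of the paired interval, which is exactly 90% under the model.

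The 90% intervals are the only inferential output for F and Fa, as no hypothesis is tested. What is at stake is whether the stated confidence level is right, and whether the width reported for this one trial depends on a software default that the SAP does not mention. Fa is the more exposed of the two, because its values come from urine collections in different periods. For F, both AUCs come from the same man in the same period and share his clearance.

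**Working it through.** **Inputs.** Six complete pairs (Protocol 9.5, if all complete Period 2); two-sided 90% level, REML, Kenward-Roger and random participant (SAP 5.2.3, Appendix 1). *Assumptions:* the within-participant correlation ρ of the two log values, which is varied from 0 to 0.9; normal log values with equal oral and IV variance; and default PROC MIXED behaviour (variance bounded at zero, 10 df once it is zero). That behaviour is a property of the software and is not written in the documents. It was reproduced in closed form, not run in SAS.

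**Plan's own figure.** The only figure to check against is the nominal 90%. The sample size has no formula to reproduce.

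**Formulas for six complete pairs.** Let MSB and MSW be the between- and within-participant mean squares, each with 5 df.

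- REML participant variance = (MSB − MSW)/2 if positive, otherwise 0.
- If MSB > MSW: half-width = t(0.95, 5) × √(2·MSW/6), which is the paired-t interval.
- If MSB ≤ MSW: half-width = t(0.95, 10) × √(2·[(MSB + MSW)/2]/6), which is unpaired.
- Chance of a zero estimate = P(F(5,5) < (1 − ρ)/(1 + ρ)).

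**Width when the bound is hit.** The pooled mean square cannot exceed MSW, so on the log scale the ratio to the paired half-width is at most t(0.95, 10)/t(0.95, 5) = 1.812/2.015 = 0.899. Its simulated average is 0.79 at ρ = 0 and 0.81 at ρ = 0.5, hence about 20% narrower.

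**Coverage over repeated trials** (2,000,000 simulated trials per row):

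| ρ | Variance set to 0 | Coverage, bounded fit | Coverage, paired-t |
|---|---|---|---|
| 0 | 50.0% | 87.3% | 90.0% |
| 0.1 | 41.6% | 87.9% | 90.0% |
| 0.2 | 33% | 88.5% | 90.0% |
| 0.3 | 26% | 88.9% | 90.0% |
| 0.5 | 12.7% | 89.6% | 90.0% |
| 0.7 | 4.0% | 89.9% | 90.0% |
| 0.9 | 0.3% | 90.0% | 90.0% |

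Repeat simulations agree to about 0.1 point, and the zero-variance rates match the exact F probability.

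**Where the shortfall sits.** At ρ = 0, trials that hit the bound are covered 90.0% of the time and the others about 84.5%: 0.50 × 90.0 + 0.50 × 84.5 = 87.25. The trials that miss the bound are those in which MSW happened to be small relative to MSB, so their intervals tend to be short. The paired interval covers about 95.5% in the boundary trials, which brings the average back: 0.50 × 95.5 + 0.50 × 84.5 = 90.0.

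**Sensitivity at ρ = 0.** Keeping 5 df at the bound gives 88.7%. An oral-to-IV variance ratio of 2 or 4 gives 87.2%. Five complete pairs give 87.0%, and four give 86.7%.

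**The case against.** - **The 87% is a corner case.** A reader might infer that the planned intervals cover only 87%. The documents do not support that. The figure needs zero correlation between a man's two values, and no correlation is given. Protocol 4.2 assumes that distribution, metabolism and excretion do not change with route, and both parts of the Fa ratio are urinary radioactivity from the same man. That points to a positive correlation for Fa as well as F. This stands.
- **Homogeneity cuts both ways.** Protocol 4.2 cites "the desire to enroll a homogeneous population due to the small sample size of this study", and lower between-man variance does make a zero estimate more likely. The same section also gives reduced intra-individual variability as a design aim, which works in the opposite direction. The quote alone does not show a low correlation. This stands.
- **The boundary trials are not the under-covered ones.** It is tempting to say that the interval fails when the variance is set to zero. It does not: coverage in those trials is about 90% or more. The paired interval restores the average by over-covering there. This stands, and is a cost of the fix.
- **The code is only an example.** This carries little weight, because the text of SAP 5.2.3 names the same procedure, estimation method and df method, and adds no rule for a zero estimate.
- **No decision depends on it.** No hypothesis or decision rule is attached, point estimates do not move with complete pairs, and individual F and Fa values will be listed, so a reader could compute the paired interval. This limits the importance but does not make the stated confidence level right.

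**Conclusion.** The point holds as a small gap in pre-specification. With six complete pairs, the bounded fit has coverage between 87.3% (zero correlation, the lowest the model's own parameter space allows) and 90.0%. The shortfall is about 1.5 points at a correlation of 0.2 and 0.4 at 0.5. Since a positive correlation is likely, the practical loss is probably under 1 to 2 points, and smaller for F than for Fa. It is a property of the procedure over repeated trials, not of the trials that hit the bound. For this one trial, the visible effect would be an interval about 20% narrower on the log scale than the paired interval, should the bound be hit.

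This rests on complete pairs, normal log values, an assumed correlation and default PROC MIXED behaviour. If 5 df were kept at the bound, the minimum would be 88.7%. The documents do not support a claim that the intervals for F and Fa are materially invalid.

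**What to change.** In SAP 5.2.3 and Appendix 1, do one of the following for the F and Fa models:

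- add the option to the procedure call, `proc mixed data=tab.pk nobound;`, or
- state that, if the participant variance is estimated as zero, the reported interval is the paired-t 90% CI on the within-participant log ratio, using participants with both values.

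With complete pairs, either change gives the paired-t interval with 5 df and 90.0% coverage at every correlation simulated. Point estimates do not change, and nothing changes unless the bound would have been hit. The cost is one option or one sentence, plus a wider interval in those cases: at least 11% on the log scale (1/0.899 = 1.11), and conservative given that the bound was hit.

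Equality with the paired-t interval does not extend to incomplete pairs. If a man contributes only one of the two values, NOBOUND and the paired-t rule can differ, so the SAP should say which applies.

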Appendix 2. Categorical Classes for ECG and Vital Signs of Potential Clinical Concern

Categories for QTcF

Absolute value of QTcF (msec)	>450 and \leq 480	>480 and \leq 500	>500
Increase from baseline in QTcF (msec)	>30 and \leq 60	>60	

Categories for PR and QRS

PR (ms)	max. \geq 300	
PR (ms) increase from baseline	Baseline >200 and max. \geq 25% increase	Baseline \leq 200 and max. \geq 50% increase
QRS (ms)	max. \geq 140	
QRS (ms) increase from baseline	\geq 50% increase	

Categories for Vital Signs

Systolic BP (mm Hg)	min. <90	
Systolic BP (mm Hg) change from baseline	max. decrease \geq 30	max. increase \geq 30
Diastolic BP (mm Hg)	min. <50	
Diastolic BP (mm Hg) change from baseline	max. decrease \geq 20	max. increase \geq 20
Supine pulse rate (bpm)	min. <40	max. >120

Measurements that fulfill these criteria are to be listed in the report.

Appendix 3. List of Abbreviations

Abbreviation	Term
AE	adverse event
AMS	accelerated Mass Spectrometry
AUC	area under the curve
AUC _{inf}	area under the concentration-time curve from time zero extrapolated to infinity
AUCl _{ast}	area under the concentration-time curve from time zero to the last measurable concentration
BLQ	below the limit of quantitation
BP	blood pressure
C _{max}	maximum observed concentration
CL	clearance
CL/F	oral clearance
CRF	case report form
CSR	clinical study report
CRU	clinical research unit
CV	coefficient of variation
dn	dose normalized
ECG	electrocardiogram
F	oral bioavailability
F _a	fraction absorbed
LLQ	lower limit of quantitation
ICH M3 (R2) MIST	international conference on harmonization M3 revision 2 for metabolites in safety testing
IP	investigational product
IV	intravenous
LS/MS/MS	liquid chromatography with tandem mass spectrometry
MRT	mean residence time
N/A	not applicable
NC	not calculated
ND	not done
NS	no sample
PK	pharmacokinetic(s)
PO	oral route
QTcF	corrected QT (Fridericia method)
REML	restricted maximum likelihood
SAP	statistical analysis plan
SD	standard deviation
T _{max}	time of maximum concentration
t _½	half-life
V _{ss}	steady state volume of distribution
V _{Z/F}	apparent volume of distribution during terminal phase
